## **9.13 End of 2nd Study Arm (Visit 8b)**

Sixteen weeks after the start of the second treatment arm (Visit 7) subjects will have completed the primary study phase. Study devices will be downloaded. A blood sample will be taken for measurement of HbA1c (see section 12.2.1). Body weight and height measurements will be made. Parents/carers will be asked to complete questionnaires (see section 12.3). Parents/carers who were interviewed at the end of the 1st arm of the study will be re-interviewed (see section 12.4).

This will be the end of the primary phase 8-month study period and subjects who are not continuing with the extension phase will return to their normal diabetes care. These subjects/guardians will be asked to return the study devices used, and will revert to their conventional insulin therapy by switching back to the insulin pump they were using before entering the study.

## **9.14 Extension Phase (UK sites only)**

At the primary phase final study visit, participants on sensor-augmented pump therapy as their standard clinical care will have the option to continue using automated hybrid closed loop system for a further 18 months in the extension phase. Parents/guardians of participants opting to continue with the extension phase will be asked to re-consent. Participants who had sensor-augmented pump therapy during the second arm of the primary phase will receive refresher training and recommence use of the automated hybrid closed loop system.

### **9.14.1 Routine Follow-up Contacts**

Parents/guardians will be contacted every 3 months during the extension phase. This can be at routine clinic appointments or by email/telephone. The purpose of this contact would be to troubleshoot any problems, and to record any adverse events, device deficiencies, changes in insulin requirements, other medical conditions and/or medication. Local or point-of-care HbA1c values will be recorded at these contacts. Throughout the extension phase, parents/guardians and/or the clinical team are free to adjust insulin therapy as per usual clinical practice, but no active treatment optimisation will be undertaken by the study team.

### **9.14.2 End of Extension Phase (Visit 9)**

At 18 months after the end of the primary study phase, parents/guardians will be asked to complete questionnaires as outlined in section 12.3. A blood sample will be taken for measurement of HbA1c (see section 12.2.1). Height and weight will be recorded. Adverse events, device deficiencies, changes in insulin requirements, other medical conditions and/or medication will be recorded.

Participants will return all study devices and will transition to usual care as described in section [9.13](#).

## **9.15 Participant Withdrawal Criteria**

The following pre-randomisation withdrawal criteria will apply:

1. Subject/guardian is unable to demonstrate safe use of study insulin pump and CGM as judged by the investigator
2. Subject/guardian fails to demonstrate compliance with insulin pump and CGM during run-in

The following pre- and post-randomisation withdrawal criteria will apply:

3. Subjects/guardians may terminate participation in the study at any time without necessarily giving a reason and without any personal disadvantage
4. Significant protocol violation or non-compliance
5. Any severe hypoglycaemia event related to the use of the closed loop system
6. Two severe hypoglycaemia events not related to the use of the closed loop system
7. DKA unrelated to infusion site failure and related to the use of the closed loop system
8. Decision by the investigator or the sponsor that termination is in the subject's best medical interest
9. Allergic reaction to insulin
10. Allergic reaction to adhesive surface of infusion set or glucose sensor

Efforts will be made to retain subjects in follow up for the final primary endpoint assessment even if the intervention is discontinued, unless the investigator believes that it will be harmful for the subject to continue in the trial. Subjects/guardians who are withdrawn for reasons stated in (4) to (10) will be invited to provide a blood sample at the end of the planned study intervention for the assessment of HbA1c.

Subjects/guardians who discontinue study intervention prior to the final visit will receive an exit survey and may be invited for an interview.

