# 10 Endpoints

## 10.1 Primary Endpoints

The primary endpoint is the between group difference in time spent with sensor glucose levels between 3.9 to 10.0 mmol/l (70 to 180 mg/dl) during the 4 months intervention period.

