86            ○ Emotional Problems Subscale  
87            ○ Conduct Problems Subscale  
88            ○ Hyperactivity Subscale  
89            ○ Peer Problems Subscale  
90            ○ Prosocial Subscale  
91            ○ Total Difficulties Score

92       13) Hypoglycemia Fear Survey  
93            ○ Behavior Subscale  
94            ○ Worry Subscale

95       14) WHO-5

96       15) Epworth Sleepiness Scale

97       16) Pittsburgh Sleep Quality Index  
98            ○ Subjective Sleep Quality Subscale  
99            ○ Sleep Latency Subscale  
100           ○ Sleep Duration Subscale  
101           ○ Habitual Sleep Efficiency Subscale  
102           ○ Sleep Disturbances Subscale  
103           ○ Use of Sleeping Medication Subscale  
104           ○ Daytime Dysfunction Subscale

105       17) Children's Sleep Habit Questionnaire  
106           ○ Bedtime Resistance Subscale  
107           ○ Sleep Onset Delay Subscale  
108           ○ Sleep Duration Subscale  
109           ○ Sleep Anxiety Subscale  
110           ○ Night Waking Subscale  
111           ○ Parasomnias Subscale  
112           ○ Sleep Disordered Breathing Subscale

113                   ○ Daytime Sleepiness Subscale

114   All metrics listed above will be outcomes in the main study. In the extension phase, the same  
115   outcomes will be analyzed, with the exceptions of the Pittsburgh Sleep Quality Index and the  
116   Children's Sleep Habit Questionnaire. The primary outcome in the extension phase will be time  
117   in range calculated over the full 18 months.

118   **4.1 Calculation of CGM Metrics**

119   For the primary outcome and all secondary CGM metrics, a single value will be calculated for  
120   each subject for each period by pooling all CGM readings between the treatment initiation visit  
121   and up to 112 days post-initiation visit or the end of treatment visit, whichever comes first. All  
122   glucose sensor readings will be weighted equally in the pooled percentages regardless of how  
123   they distribute across weeks. Data will not be truncated due to protocol deviations.

124   Baseline CGM metrics will be calculated by pooling all readings up to the last 14 available days  
125   of CGM readings prior to randomization.

126   In the extension phase, CGM metrics will be calculated by pooling all readings inclusively  
127   occurring from the day after the last visit of the main study up until the last visit of the extension  
128   phase.

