129   Additionally, CGM metrics will be calculated every three months during the extension phase by  
130   inclusively pooling all CGM readings falling within each of the windows specified at each month  
131   in the table below:

Month	Window for Analysis
Month 3	Days 1-91
Month 6	Days 92-182
Month 9	Days 183-274
Month 12	Days 275-365
Month 15	Days 366-456
Month 18	Days 457-548

132

133   **4.2 Calculation of BMI SD Scores**

134   BMI standard deviation score will be calculated using the WHO growth chart.

135   **5. Analysis Datasets and Sensitivity Analyses**

136   **5.1 Analysis Cohorts**

- 137   • The primary analysis and all secondary analyses will be performed on a modified  
138   intention-to-treat basis with each day included in the treatment group assigned by  
139   randomization.
- 140   • A per-protocol analysis restricted to randomized participants with a minimum of 60% of  
141   available CGM readings during the control period and 60% CL system use during the CL  
142   period will be conducted for the primary outcome.
- 143   • Safety outcomes will be reported for all enrolled participants, regardless of whether the  
144   study was completed.

145 **6. Analysis of the Primary Efficacy Endpoint**

146 **6.1 Included Subjects**

147 In analyses conducted in the main study, only subjects with at least 168 hours of CGM data in at  
148 least one period will be included. If a subject has more than 168 hours of data in period 1 and  
149 then drops out of the study without any data in period 2, then he or she will be included in the  
150 analysis.

151 In the extension phase, analyses will include participants with at least 168 hours of CGM data  
152 during the SAP phase of the main study and at least 672 hours of CGM data during the extension  
153 phase. For the analyses conducted every three months during the extension phase, at least 168  
154 hours of CGM data will be required within a given three-month period to be included in the  
155 tabulations of summary statistics for that particular period.

156 **6.2 Missing Data**

157 Missing data will not be imputed for the primary analysis in this study.

158 **6.3 Statistical Methods**

159 Mean  $\pm$  SD or summary statistics appropriate to the distribution will be reported for the primary  
160 outcome and each of the key secondary outcomes listed below over the four month period by  

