## 370 **9. Adherence and Retention Analyses**

### 371 **9.1 Utility Analysis**

372 The amount of CGM use will be tabulated for each treatment arm, in addition to the amount of  
373 closed loop system use in the CL arm. Summary statistics appropriate to the distribution and  
374 range will be reported for the percentage of time using the CGM over the four month period (as  
375 defined above) for each treatment group. The same will be done for the percentage of time using  
376 the closed loop system in the CL arm. Tabulations of summary statistics will also be performed  
377 for the percentage of time spent using the closed loop system while using the CGM in the CL  
378 arm.

379 The percentage of time spent using the CGM will be calculated by dividing the total number of  
380 CGM readings by the expected number of readings during the four-month period. The  
381 percentage of time using the closed loop system in the CL arm will be calculated by dividing the  
382 total amount of time that temporary basal infusion lasts no more than 30 minutes by the  
383 maximum possible amount of time that the system could have been used. The percentage of time  
384 using the closed loop system while using the CGM (in the CL arm) will then be computed by  
385 dividing the time that the closed loop system was operational by the amount of time that the  
386 CGM was available.

387 If a subject drops out of the study in the middle of a period, then the subject will be counted as  
388 not using the CGM or the closed loop system at all during the remainder of the study. Thus, these  
389 time points will be counted as zero use in the calculation of CGM use and closed loop system  
390 use.

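### Protocol 9.15 ties follow-up after stopping to a final assessment that a period-long CGM endpoint does not have, and nowhere asks for the study CGM to continue

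*Combined protocol and SAP*

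**What the plan says.** **Follow-up after stopping.** Protocol 9.15 states: "Efforts will be made to retain subjects in follow up for the final primary endpoint assessment even if the intervention is discontinued", with an exception where the investigator thinks continuing in the trial would be harmful. Children withdrawn under items 4 to 10 "will be invited to provide a blood sample at the end of the planned study intervention for the assessment of HbA1c". An exit survey and a possible interview are also mentioned. Continued CGM is not.

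**The endpoint.** Protocol 10.1 defines it as the between-group difference in "time spent with sensor glucose levels between 3.9 to 10.0 mmol/l (70 to 180 mg/dl) during the 4 months intervention period". SAP 4.1 computes one value for "each subject for each period by pooling all CGM readings between the treatment initiation visit" "and up to 112 days post-initiation visit or the end of treatment visit, whichever comes first", with all readings weighted equally and no truncation for protocol deviations.

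**The analysis.** SAP 5.1 uses a modified "intention-to-treat basis with each day included in the treatment group assigned by" randomisation. SAP 6.1 admits a child with at least 168 hours of CGM data in at least one period. SAP 6.2 rules out imputation for the primary analysis. The only alternative analysis in SAP section 5 is per-protocol, requiring 60% CGM data in the control period and 60% closed loop use in the closed loop period.

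**The concern.** The retention sentence in 9.15 would suit an outcome measured once at a closing visit. For an outcome built up reading by reading over four months, a site can follow 9.15 to the letter, see the child at the planned end, take the HbA1c sample, and still add nothing to the primary endpoint for the weeks after stopping. HbA1c is a key endpoint, not the primary one.

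Counting every day in the randomised group helps only for days that have readings. If the sensor comes off when the intervention stops, the child's value for that period describes the time on the intervention. For closed loop this tends to flatter the result, since the weeks without it are missing.

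The loss may also differ by arm: withdrawal items 5 and 7 in 9.15 concern only events related to closed loop use. Readings never collected cannot be restored at analysis.

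**Working it through.** **1. The plan's own figure.** Inputs from Protocol 14.12 and SAP 3: effect 5 points, SD 10.3, between-period correlation 0.3, 90% power; two-sided alpha 0.05 from Protocol 14.2.

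- SD of the within-child difference = 10.3 × √(2 × (1 − 0.3)) = 12.19.
- The normal approximation gives n = 62.4, so 63. The noncentral t gives 65, with power 90.3%.
- 65 × 1.10 = 71.5, so 72.

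The plan's 65 and 72 are reproduced. This point does not touch the sample size.

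**2. The inclusion floor.** 168 hours out of 112 × 24 = 2,688 hours is 6.25% of a period. A child who stops after one week and removes the sensor can enter the primary analysis with the other 93.75% of the period missing.

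**3. Two kinds of child who stop closed loop.**

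| | Study CGM continues | Study CGM stops |
|---|---|---|
| Readings after stopping | Pooled under closed loop (SAP 4.1, 5.1) | None exist |
| Value for the period | On and off closed loop, as intended | Pre-stop readings only |
| Shift in the estimate | Zero | Depends on how many children and how much of the period |

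No section of either document asks for the left-hand column. SAP 4.1 also closes the window at the end-of-treatment visit if that comes before day 112, and does not say whether a visit brought forward because of discontinuation counts as that visit.

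**4. Size of the shift.** Assumptions not given in the documents: a share q of children stop closed loop; a share m of the closed loop period is then missing; time in range after stopping returns to control level, 5 points lower (the planned effect); no offsetting loss arises in the control arm. Then

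overstatement = q × m × 5 points.

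For scale, the standard error with 72 full pairs is 12.19 / √72 = 1.436.

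| q (children of 72) | m | Overstatement | In standard errors |
|---|---|---|---|
| 5% (3.6) | 50% | 0.05 × 0.50 × 5 = 0.13 | 0.09 |
| 10% (7.2) | 50% | 0.10 × 0.50 × 5 = 0.25 | 0.17 |
| 10% (7.2) | 87.5% | 0.10 × 0.875 × 5 = 0.44 | 0.30 |
| 10% (7.2) | 93.75% (168-hour floor) | 0.10 × 0.9375 × 5 = 0.47 | 0.33 |

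**5. Precision.** A two-period crossover model with the same SD and correlation, and normal-approximation power for 5 points, gives:

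- 72 full pairs: SE 1.436, power 93.6%
- 65 pairs plus 7 children with period 1 only: SE 1.484, power 92.1%
- 65 pairs alone: SE 1.512, power 91.1%

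All exceed the planned 90%. The SAP 6.3 model also uses baseline as a third record, which these figures ignore.

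**The case against.** A reader might infer that 9.15 keeps children for one closing assessment only, that all readings after stopping are lost, and that the intention-to-treat estimate therefore becomes an on-treatment one. The documents do not support this.

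- 9.15 does not restrict follow-up to one assessment. Its default is to stay in the trial, and since the endpoint is CGM, retention can be read to include CGM. The HbA1c sentence sets no limit on what retained children provide.
- SAP 4.1 and 5.1 pool every in-window reading under the assigned arm without truncation. Families are trained to switch between closed loop and sensor augmented pump therapy (Protocol 9.8.1), and the control arm uses the study pump and CGM (9.8.2). A child who stops closed loop and keeps these devices is analysed by intention to treat.
- SAP 9.1 counts a child as "not using the CGM or the closed loop system at all during the remainder of the study", but only for one who drops out of the study, and only for the use percentages. It does not show that the plan expects CGM to end when closed loop ends.
- The 10% in Protocol 14.12 is dropout, not stopping of closed loop. Families may leave without giving a reason (item 3), and no rewording recovers their readings.
- Only two withdrawal items are specific to closed loop. No closed-loop-related severe hypoglycaemia or ketoacidosis occurred among the 23 children in the pilot, though its periods lasted only 21 days.
- Power stays above 90% in every case examined, so loss of precision is not an argument.

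All of this stands and narrows the point. What it leaves untouched is that continued CGM after stopping is implied at best. Whether the readings exist is left to site and family, although the intention-to-treat analysis depends on them.

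**Conclusion.** The point holds in a limited form. The 9.15 wording does not fit the endpoint, neither document asks for CGM after discontinuation, and SAP 4.1 is silent on an early end-of-treatment visit. The consequence is confined to children whose CGM stops: their value rests on pre-stop readings, with a floor of 168 hours and no imputation. For children who keep the study CGM the SAP is already right.

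The likely overstatement is about 0.13 to 0.44 points of the planned 5, or 0.09 to 0.30 standard errors. It rests on assumed stopping rates of 5% to 10%, 50% to 87.5% of the period missing, and return to control level. The upper end treats the whole dropout allowance as children who stop closed loop and have no later CGM. This would not by itself overturn a 5-point result. The case for changing the text is that a small, avoidable bias can be reduced at little cost, and only while data are being collected.

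**What to change.** **Protocol 9.15.** Replace the reference to a final primary endpoint assessment with a request that children who stop the assigned intervention, including those withdrawn under items 4 to 10, continue to wear and upload the study CGM to day 112 of that period, where the investigator judges it safe and the family agrees.

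**SAP 4.1.** State that an end-of-treatment visit held early because of discontinuation does not close the data window, and that readings after stopping are pooled under the assigned arm.

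The withdrawal criteria, treatment after stopping and entry to the second period are left as they are; this is a request for data only.

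**Cost.** Two short wording changes and sensors for a few more children. Uptake will be incomplete, for example after adhesive allergy or full withdrawal of consent. The estimate may come out slightly less favourable to closed loop.

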## **14.2 Other Key Endpoints**

For the following key endpoints, the familywise type I error rate (FWER) will be controlled at two sided  $\alpha = 0.05$ . A gatekeeping strategy will be used, where the primary endpoint will be tested first, if passing the significance testing, other key endpoints will be tested in the order listed below using the fixed-sequence method at  $\alpha = 0.05$ .

- Time spent with sensor glucose levels between 3.9 to 10.0 mmol/l (70 to 180 mg/dl)
- Time spent above target glucose (10.0 mmol/l) (180 mg/dl)
- HbA1c
- Average of glucose levels
- Time spent below target glucose (3.9 mmol/l) (70 mg/dl)

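### Protocol 9.15 makes no provision for an HbA1c sample from families who leave by choice, so a gated endpoint carries a small amount of avoidable missing data

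*Combined protocol and SAP*

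**What the plan says.** Protocol 9.15 numbers its withdrawal reasons. (1) and (2) apply before randomisation only; (3) to (10) apply both before and after it. Reason (3) reads "Subjects/guardians may terminate participation in the study at any time without necessarily giving a reason and without any personal disadvantage". Three provisions then deal with what happens after a child stops:

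- Retention, with no limit by reason: "Efforts will be made to retain subjects in follow up for the final primary endpoint assessment even if the intervention is discontinued". The only outcome it names is the primary endpoint, which is CGM time in range.
- HbA1c, limited by reason: "Subjects/guardians who are withdrawn for reasons stated in (4) to (10) will be invited to provide a blood sample". The sample is due when the planned intervention would have ended.
- Exit survey, with no limit by reason: "Subjects/guardians who discontinue study intervention prior to the final visit will receive an exit survey and may be invited for an interview".

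On HbA1c as an endpoint, protocol 14.2 says that "the familywise type I error rate (FWER) will be controlled at two sided" 0.05 and that "other key endpoints will be tested in the order listed below using the fixed-sequence method". HbA1c is third of five, after time in range and time above 10.0 mmol/l. SAP 6.3 stops formal testing at the first non-significant result. SAP 7.2 handles a missing end-of-period HbA1c by direct likelihood from earlier measurements, and SAP 7.4.3 models baseline, period 1 and period 2. SAP 7.3 accepts an outcome value only within 7 days either side of the end of treatment visit.

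**The concern.** HbA1c is more exposed to early departure than the CGM endpoints. A child who leaves mid-period still contributes CGM outcomes if 168 hours were recorded (SAP 6.1), because SAP 4.1 pools whatever was captured. HbA1c is a single value at the end of the period. A child who leaves in period 1 without that sample has only a baseline value.

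Direct likelihood is valid if missingness is explained by the observed values. In an open-label device trial, a family's choice to leave could depend on how the child was doing on the assigned arm in ways that earlier HbA1c does not capture. The SAP plans no sensitivity analysis for missing HbA1c, and SAP 7.2 itself says that every method for missing data rests on assumptions that cannot be tested and that the aim is to have few missing values. Not asking willing families for the sample works against that aim. A distorted HbA1c result also matters further down the sequence, because mean glucose and time below 3.9 mmol/l are formally tested only if HbA1c is significant.

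**Working it through.** **Wording.** Set against the numbered list, the exit survey covers anyone who discontinues early, whatever the reason; the HbA1c invitation covers (4) to (10); the retention sentence covers any reason but names only the CGM endpoint. The text therefore has no HbA1c provision for reason (3), although a contact with these families is already planned.

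**The plan's own figure.** Protocol 14.12 gives a 5-point effect, SD 10.3, between-period correlation 0.3 and 90% power.

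- SD of the paired difference: 10.3 × √(2 × (1 − 0.3)) = 12.19.
- Normal approximation: (12.19 × (1.960 + 1.282) / 5)² = 62.4, so 63.
- Noncentral t: power is 89.8% at n = 64 and 90.3% at n = 65, so 65 is reproduced.
- Dropout: 65 × 1.10 = 71.5, so 72 is reproduced. The allowance is 72 − 65 = 7 children, 7/72 = 9.7%, for all reasons together.

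This sizing is for time in range. No HbA1c SD, effect or expected missingness is stated, so power for HbA1c cannot be computed.

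**Size of a possible shift.** Let L be the number of children who leave one arm under (3) without a sample. Let D be the amount by which their HbA1c differs from what the analysis in effect assumes. The arm mean then shifts by (L/72) × D. Both L and D are assumptions; the documents give no figure for either.

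| L | L/72 | D = 0.3 | D = 0.5 | D = 1.0 |
|---|---|---|---|---|
| 1 | 0.0139 | 0.004 | 0.007 | 0.014 |
| 3 | 0.0417 | 0.012 | 0.021 | 0.042 |
| 5 | 0.0694 | 0.021 | 0.035 | 0.069 |
| 7 | 0.0972 | 0.029 | 0.049 | 0.097 |

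For orientation, the protocol's adult 12-week crossover trial (section 4.3.2, Table 7) shows 7.6 − 7.3 = 0.3 points. The bottom row is 0.029/0.3 = 10% to 0.097/0.3 = 32% of that; it puts every allowed dropout under (3), in one arm, shifted in one direction. Similar losses from both arms would largely cancel in the treatment difference.

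**Whether a sample would count.** SAP 7.3 centres its window on the end of treatment visit and names no substitute date when that visit does not happen. SAP 8.3 does supply one, the dropout date, for safety analyses. In a crossover, the protocol's reference to the planned end of the intervention could also mean the current period or the whole study. An extra sample might therefore be collected and then fall outside the analysis.

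**The case against.** The strongest reply is that reason (3) means ending participation in the study, not just stopping the device, so leaving these families off the list respects their decision. Children who stop the device but stay in follow-up come under the retention sentence and would reach Visit 6 or 8b, where HbA1c is drawn. This stands in part: some families will decline, and any invitation must allow for that. It does not explain why the same families can be sent an exit survey but not asked for a sample.

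Three stronger readings are tempting, and the documents do not support them.

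- A reader might infer that no outcome sample can come from these families. Section 9.15 does not bar one; it only fails to arrange it.
- A reader might infer that those leaving under (3) are the families most dissatisfied with their arm. The documents give no number, motive or arm split for reason (3), and several treatment-related withdrawals, such as closed-loop-related severe hypoglycaemia or DKA, are among the invited reasons.
- A reader might infer that these children are lost from the HbA1c analysis. A child who leaves in period 2 would normally have given a period 1 value, and the likelihood model keeps partial records.

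It is also fair to say that a sample taken after a child has left partly reflects usual care, so it would not recover the on-arm value that the shift calculation describes. It would inform a comparison by assigned treatment, and the plan already accepts the same limitation for reasons (4) to (10).

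**Conclusion.** The gap is real and modest. Section 9.15 seeks an HbA1c sample after every kind of post-randomisation withdrawal except a family's own choice, and this leaves avoidable missing data in a gated endpoint whose analysis relies on missing at random. The effect is probably small: a worst case of about 0.03 to 0.10 points, and about 0.004 to 0.042 points with 1 to 3 leavers. These figures rest on the assumed 0.3 to 1.0 point difference and on all such leavers coming from one arm. The primary endpoint's sample size is not in question: 65 remaining of 72 still gives 90.3% power. The case for change rests on low cost and on consistency with the plan's own approach, not on evidence that the HbA1c result would be biased.

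**What to change.** 1. In protocol 9.15, extend the HbA1c invitation from reasons (4) to (10) to reasons (3) to (10), unless the family declines further contact.
2. In the same sentence, state that the sample is due at the planned end of the period in which the child left.
3. In SAP 7.3, add that when no end of treatment visit occurs, the 7-day window is centred on that planned date and the value is analysed under the randomised assignment.

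The cost is one sentence in each document, matching consent wording, and one finger-prick sample in a few families, some of whom will decline. The value will partly reflect time off the assigned arm.

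The SAP's revision history marks the initial analyses as completed at version 3.0. If primary-phase collection has closed, what remains is to report missing HbA1c by arm, period and withdrawal reason, and to add a sensitivity analysis that allows data to be missing not at random, for example over the 0.3 to 1.0 point range used above.
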